### 4.2. PACKAGING AND LABELING

The test medications will consist of Sildenafil 20 mg tablets (Revatio®) and Placebo tablets that resemble Revatio®. These medications will be shipped in bulk containers to the Lucile Packard Children's Hospital (LPCH) Pharmacy where they will be stored.

Each bottle will be labeled in accordance with Good Manufacturing Practice and will include the following information:

- Study Acronym Name
- Unique alpha-numeric identifier (Lot number)
- Storage requirement
- Investigational use and appropriate caution statements
- Sponsor identification
- Unique subject ID

The LPCH Pharmacy will dispense the Revatio® or Placebo in bottles labeled with the subjects identification information based upon the randomized code. The LPCH Pharmacist will compound an extemporaneously prepared oral suspension from Revatio® 20mg tablets or placebo tablets, depending on subject's preference.

Pharmacy staff will know if the subject is receiving Placebo or Revatio®. Depending on subjects weight, the study pharmacist will formulate study drug into an oral suspension for 2.5mg per ml dosing volume.

Subjects who weigh 8kg – 20kg will receive a 4-week supply 10mg/4ml TID, and the treatment will be compounded into a 480ml dosing volume, and then transferred to four bottles of 120 ml each.

Subjects weighing more than 20kg will receive a 4-week supply 20mg/8ml TID. The subject and the research physician will be blinded to Placebo or Revatio® until completion of the 20 week study visit. The code will also be broken in the situation of a Serious Adverse Event.

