### **10.3. SAFETY**

All subjects who receive study medication will be evaluable for the safety analysis. Summary statistics will be provided with respect to patients requiring discontinuation from treatment and from study (any reason and for safety reasons). AE summaries will focus on treatment-emergent AE and will summarize subject AE incidences by severity, seriousness, and relationship to treatment. Vital signs, laboratory tests, and concomitant medication usage will be displayed as listings by subject.

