### **12.5. ASSESSMENT OF ADVERSE EVENT SEVERITY, CAUSALITY, AND EXPECTEDNESS**

Unexpected AE: Any adverse event, the specificity or severity of which is not consistent with the risk information described in the Investigator's Brochure.

Severity: Severity of the AE will be determined by the investigator. Severity may be mild, moderate, or severe:

- Mild – An event is mild if the subject is aware of, but can easily tolerate the sign or symptom
- Moderate – An event is moderate if the sign or symptom results in discomfort significant enough to cause interference with the subject's usual activities
- Severe – An event is severe if the sign or symptom is incapacitating and results in the subject's inability to work or engage in their usual activities

In addition, the Investigator will determine if the adverse event is may have been caused by the test product. The following circumstances would be considered to be possibly related:

- A single occurrence of an event that is uncommon and known to be strongly associated with drug exposure (e.g., angioedema, hepatic injury, Stevens-Johnson Syndrome).
- One or more occurrences of an event that is not commonly associated with drug exposure, but is otherwise uncommon in the population exposed to the drug (e.g., tendon rupture).
- An aggregate analysis of specific events observed in a clinical trial (such as known consequences of the underlying disease or condition under investigation

or other events that commonly occur in the study population independent of drug therapy) that indicates those events occur more frequently in the drug treatment group than in a concurrent or historical control group.

In source documentation, causality will be recorded using the following definitions:

- Not Related – An event is considered to be not related to the use of the test medication when the event is DEFINITELY UNRELATED or UNLIKELY to have any relationship to the use of the test medication
- Possibly Related – An event is considered to be possibly related to the use of the test medication when there is a REASONABLE POSSIBILITY that the test medication caused the adverse event

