## **12.6. UNBLINDING OF TEST MEDICATION**

If a subject develops an adverse reaction that requires withdrawal from the study we will document whether they are receiving placebo or active medication. The treatment assignment will also be unblinded during the twenty week visit after the MRI examination is completed.

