| Hearing exam                                  | x             |  |   |  |   |  |   | x                                       |   |
| Administer and dispense study medication      |                             | x  |   | x  |   | x  |   |   |   |
| Monitor vital signs every 30 mins for 2 hours |                             | x  |   |  |   |  |   |   |   |
| Collect unused study medication               |                             |  |   | x  |   | x  |   | x   |   |
| Dispense or review medication diary           |                             | x  |   | x  |   | x  |   | x   | x   |
| End of treatment                              |                             |  |   |  |   |  |   | x   |   |
| MRI   | x                           |  |   |  |   |  |   | x   |   |
| Review adverse events                         |                             | x  | x   | x  | x   | x  | x   | x   | x   |
| Unblind treatment                             |                             |  |   |  |   |  |   | x                                       |   |
| End of study/ Exit form                       |                             |  |   |  |   |  |   |   | x   |

 The "-A" suffix at end of Visit name indicates visits that are for the crossover Active Treatment Period, an option offered to any subject who received placebo during the Original Treatment Period.

 At Week 20, treatment will be unblinded and if subject received placebo then they have the option to enter the Active Treatment Period. Unblinding is performed only at the Week 20 Visit of the Original Treatment Period.

 If subject is female who has reached menarche.

 If hearing exam is not successful at screening, it will be repeated at subsequent visits until a satisfactory hearing test result is obtained.

 Subjects who exit early will not have a final MRI but we will attempt to obtain a Urine Pregnancy Test.

 Subjects local to a cooperating research site will attend Week 4, Week 12, and Week 32 visits at their cooperating site.

 Subjects local to a cooperating research site will be offered the option to have this procedure at their cooperating site or at Stanford.

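### For serious adverse events, and possibly for withdrawals after an adverse reaction, severity and relationship can be rated with the arm known, because the plan does not require the rating to be recorded before the code is broken

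*Combined protocol and SAP*

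**What the plan says.** All references are to the combined protocol and SAP.

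- **Blinding and code breaks.** Section 4.2: "The subject and the research physician will be blinded to Placebo or Revatio® until completion of the 20 week study visit". It then adds: "The code will also be broken in the situation of a Serious Adverse Event". No condition is attached, and no order relative to the causality rating is given. Section 12.6: "If a subject develops an adverse reaction that requires withdrawal from the study we will document whether they are receiving placebo or active medication". A footnote to the schedule in Section 16 says: "Unblinding is performed only at the Week 20 Visit of the Original Treatment Period".
- **Who rates.** Section 12.5 has the investigator grade severity, and on causality: "the Investigator will determine if the adverse event is may have been caused by the test product". Section 12.1 has relationship to the test medication recorded for every adverse event.
- **How causality is rated.** Section 12.5 lists three circumstances that count as possibly related. The third is an aggregate analysis showing that "those events occur more frequently in the drug treatment group than in a concurrent or historical control group". The section then defines the two categories used in source documents, Not Related and Possibly Related. These turn on whether a reasonable possibility exists and do not mention group frequencies.
- **What the test medication is.** Section 4.1 identifies it as sildenafil and lists placebo separately as the control. Section 4.2 uses the plural more loosely and includes placebo tablets.
- **How the rating is used.** Under Section 10.3 the adverse event tables "will summarize subject AE incidences by severity, seriousness, and relationship to treatment". The same section summarises discontinuations for any reason and for safety reasons.

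**The concern.** Safety is a stated objective, and the randomised 20 weeks on placebo are its only concurrent control. A causality rating informs a between-arm comparison only if the rater does not know the arm. For serious events, 4.2 can reveal the arm before the rating is made. For withdrawals after an adverse reaction, 12.6 may do so.

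Knowing the arm acts unequally. If the test medication is sildenafil, a subject known to be on placebo has not taken it, so Possibly Related is in practice closed. The same event in a subject known to be on sildenafil can still be rated Possibly Related. The related-event rows of the 10.3 summary could then show more events on sildenafil even if the drug caused none of them. Severity is exposed as well, though without this built-in direction.

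**Working it through.** The plan gives no event rate, attribution rate or other figure to reproduce. The check is a reading of the sections in sequence, followed by an illustration on declared assumptions.

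**Sequence of steps as written**

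1. A serious event occurs in the randomised period. Its seriousness is already settled, because that is what triggers the code break in 4.2.
2. The code is broken (4.2).
3. Severity and relationship are rated by the investigator (12.1, 12.5). No section says whether this comes before or after step 2, asks for a blinded rater, or asks for a flag when the rating follows the break.
4. The rating enters the summary (10.3).

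For withdrawal after an adverse reaction, step 2 is weaker. Section 12.6 says only that "we will document whether they are receiving placebo or active medication". Its heading concerns unblinding, but it does not say that the rating investigator learns the arm, or when.

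**Scope.** Other adverse events up to Week 20 are rated under the blind. Events after the Week 20 visit are open by design. The exposure is therefore limited to serious events, and possibly adverse-reaction withdrawals, in the randomised 20 weeks.

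**Which rows are exposed.** The relationship rows, and the severity rows for the same events. Counts by seriousness and counts of discontinuations do not use the causality rating.

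**Illustration (assumed rates, upper range)**

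Let q be the share of subjects in each arm with an exposed event that the drug did not cause. Let rS and rP be the shares of those events rated related on sildenafil and on placebo. The artificial difference is

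D = q × (rS − rP).

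Rated blind, take rS = rP = 0.30, so D = 0. With q = 0.20 this is 0.20 × 0.30 = 6% in both arms. With the arm known, take the extreme rP = 0, and let rS stay at 0.30 or rise to 0.50.

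| q | rS = 0.30 | rS = 0.50 |
|---|---|---|
| 0.10 | 0.10 × 0.30 = 3 points | 0.10 × 0.50 = 5 points |
| 0.20 | 0.20 × 0.30 = 6 points | 0.20 × 0.50 = 10 points |
| 0.30 | 0.30 × 0.30 = 9 points | 0.30 × 0.50 = 15 points |

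A second set of assumptions, with half of events rated related when blind and q from 5% to 20%, gives 0.05 × 0.5 = 2.5 to 0.20 × 0.5 = 10 points. Both sets put placebo attribution at zero, so they show how large the effect could be and are not estimates.

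**Scale in subjects.** Section 6.1 plans 60 subjects at 2:1: 60 × 2/3 = 40 on sildenafil and 60 × 1/3 = 20 on placebo. Moving one placebo subject from related to not related shifts that arm by 1/20 = 5 percentage points.

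**The case against.** Several counter-arguments are fair.

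- **The key counts are safe.** Section 10.3 already summarises by seriousness and gives discontinuations for any reason. This stands, and it confines the problem to the rows that rest on the investigator's rating.
- **The written definitions are the same in both arms.** A reader might infer that relationship is in fact judged differently in the two arms. The documents do not say so. They show only that some ratings can be made with the arm known.
- **A break for every serious event is not settled.** Section 4.2 is unconditional, but the Section 16 footnote confines unblinding to Week 20 and 12.6 does not mention serious events. The footnote may only be excluding the Week 20-A visit. The conflict stands and must be resolved.
- **The aggregate criterion.** A reader might infer that 12.5 uses the arm comparison to set the label that 10.3 then reports. The text does not support that: the circumstance is an aggregate analysis, it also admits a historical control, and the source-document definitions do not use group frequencies. What remains is a wording fault, in that a group-level judgement sits under a sentence addressed to the investigator rating an event.
- **The figures are assumed and the trial is small.** Both are true. A 6% rate on placebo is 1.2 of 20 subjects, and at a true 6% no related event at all would occur with probability 0.94^20 = 0.29. Section 11 calls the study exploratory and descriptive, and no test on related events is planned. This argues against quoting a size. It also means that the data could not reveal the bias afterwards.
- **The Safety Monitoring Plan may contain a rule.** Sections 9 and 12.4.3 refer to it for DSMB matters. It is not among the documents, so this cannot be excluded; 12.5 and 12.6 do not point to it for causality.

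**Conclusion.** The point holds within limits. For serious events under 4.2, and possibly for adverse-reaction withdrawals under 12.6, the arm can be known before severity and relationship are rated, because no supplied section requires the rating to be recorded first. Because 4.1 identifies the test medication as sildenafil, the relationship rows for these events can be biased towards an excess on sildenafil. This rests on 4.2 being followed as written and on the absence of a contrary rule in the Safety Monitoring Plan.

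The documents do not allow an estimate of the size. The 3 to 15 points are an upper-range illustration on assumed event rates of 10% to 30% and attribution of 30% to 50% on sildenafil and none on placebo. The plan should be changed, because the gap concerns a stated objective and costs almost nothing to close. The 12.5 aggregate criterion is a secondary wording point and is not evidence of bias.

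**What to change.** 1. **Sections 12.5 and 12.6:** require the investigator to record and date severity and relationship before any non-urgent code break. Flag ratings first made after a break, and record later changes separately.
2. **Section 10.3:** summarise the rating made before the break, and identify the flagged ones. State that the main between-arm safety comparison uses all events in the randomised 20 weeks regardless of relationship. Summaries by seriousness and of discontinuations are already planned; the restriction to the randomised period and the explicit priority are new.
3. **Section 12.5:** reword so that the between-group frequency comparison belongs to aggregate review by the DSMB or sponsor and is not a ground for the per-event rating.
4. **Sections 4.2, 12.6 and the Section 16 footnote:** reconcile them on when the code is broken, and say in 12.6 who learns the arm. Which rule applies is for the sponsor to decide.

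The cost is a few sentences, one date field on the adverse event form, and one form step before a non-urgent break. Emergency unblinding is not delayed, and no additional assessor is needed.

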## **12.6. UNBLINDING OF TEST MEDICATION**

If a subject develops an adverse reaction that requires withdrawal from the study we will document whether they are receiving placebo or active medication. The treatment assignment will also be unblinded during the twenty week visit after the MRI examination is completed.

## **12.7. FOLLOW-UP OF SUBJECTS WITH ADVERSE EVENTS**

For subjects who are experiencing ongoing unresolved adverse events at the time of their study completion or early discontinuation from the study, the Investigator will schedule an appropriate follow-up visit in order to determine the outcome of the event.

## **13. INVESTIGATOR OBLIGATIONS**

The Principal Investigator will comply with the commitments outlined in the Statement of Investigator (Form FDA 1572), with current Good Clinical Practice (GCP), and with all applicable regulatory requirements as outlined in Appendix 18.2 of this protocol.

Additional information on Investigator Obligations is listed in Item 10, section 1 of the IND application.

## **14. INVESTIGATOR AND MONITOR RESPONSIBILITIES**

The Investigator will designate a monitor to conduct the appropriate site visits monitoring at the appropriate intervals. The clinical investigation will be monitored to ensure that: the rights and well being of the subjects are protected; the reported data are accurate, complete, and verifiable from the source documents; and the study is conducted in compliance with the current approved protocol, with current GCP, and with applicable regulatory requirements.

Monitoring will be conducted periodically while the clinical study is ongoing. Monitoring methods may include site visits, telephone, written and fax correspondence. The study monitor will contact the site at appropriate intervals.

## 16. STUDY PLAN

Table 16-1: Study Procedures by Treatment Day

| Visit:  | Screening
(Day -7 to +1) | Baseline &
Baseline-A 
(Day 0) | Week 2 &
Week 2-A 
(~4 1 Day) | Week 4  &
Week 4-A 
(~4 14 Days) | Week 8 &
Week 8-A 
(~4 1 Day) | Week 12  &
Week 12-A 
(~4 14 Days) | Week 16 &
Week 16-A 
(~4 1 Day) | Week 20 &
Week 20-A 
(~4 14 Days) | End of Study 
Early Exit 
(Week 32)
(~4 14 Days) |
|---|-----------------------------|--|---|--|---|--|---|---|---|
| Procedures:                            |                             |  |   |  |   |  |   |   |   |
| Informed Consent/Accent                       | x                           |  |   |  |   |  |   |   |   |
| Inclusion/Exclusion criteria                  | x                           |  |   |  |   |  |   |   |   |
| Vital signs (height, weight, HR, BP, temp)    | x                           | x  |   | x  |   | x  |   | x   | x   |
| Complete history                              | x                           |  |   |  |   |  |   |   |   |
| Interval history                              |                             | x  | x   | x  | x   | x  | x   | x   | x   |
| Physical examination                          | x                           | x  |   | x  |   | x  |   | x   | x   |
| Phone call                                    |                             |  | x   |  | x   |  | x   |   |   |
| Assessment of LM by MD                        | x                           | x  |   | x  |   | x  |   | x   | x   |
| Assessment of LM by participant               |                             |  |   | x  |   | x  |   | x   | x   |
| LM measurements                               | x                           | x  |   | x  |   | x  |   | x   | x   |
| LM photographs                                | x                           | x  |   | x  |   | x  |   | x   | x   |
| Laboratory tests                              | x               |  |   |  |   |  |   | x   |   |
| Urine pregnancy test                          | x               |  |   |  |   |  |   | x                                       |   |
| Ophthalmology exam                            | x               |  |   |  |   |  |   | x                                       |   |
| Hearing exam                                  | x             |  |   |  |   |  |   | x                                       |   |
| Administer and dispense study medication      |                             | x  |   | x  |   | x  |   |   |   |
| Monitor vital signs every 30 mins for 2 hours |                             | x  |   |  |   |  |   |   |   |
| Collect unused study medication               |                             |  |   | x  |   | x  |   | x   |   |
| Dispense or review medication diary           |                             | x  |   | x  |   | x  |   | x   | x   |
| End of treatment                              |                             |  |   |  |   |  |   | x   |   |
| MRI   | x                           |  |   |  |   |  |   | x   |   |
| Review adverse events                         |                             | x  | x   | x  | x   | x  | x   | x   | x   |
| Unblind treatment                             |                             |  |   |  |   |  |   | x                                       |   |
| End of study/ Exit form                       |                             |  |   |  |   |  |   |   | x   |

 The "-A" suffix at end of Visit name indicates visits that are for the crossover Active Treatment Period, an option offered to any subject who received placebo during the Original Treatment Period.

 At Week 20, treatment will be unblinded and if subject received placebo then they have the option to enter the Active Treatment Period. Unblinding is performed only at the Week 20 Visit of the Original Treatment Period.

 If subject is female who has reached menarche.

 If hearing exam is not successful at screening, it will be repeated at subsequent visits until a satisfactory hearing test result is obtained.

 Subjects who exit early will not have a final MRI but we will attempt to obtain a Urine Pregnancy Test.

 Subjects local to a cooperating research site will attend Week 4, Week 12, and Week 32 visits at their cooperating site.

 Subjects local to a cooperating research site will be offered the option to have this procedure at their cooperating site or at Stanford.

